##### **Secondary Outcome Measures**

- Incidence and severity of adverse events (ocular and non-ocular).
- Total number of intravitreal injections required from baseline through weeks 48-57 (week closest to week 52), baseline through week 104 and baseline through week 156.
- Total number of office visits and imaging studies performed from baseline through weeks 24-28 (week closest to week 26), baseline through weeks 48-56 (week closest to week 52), baseline through weeks 72-82 (week closest to week 78), baseline through week 104, baseline through weeks 128-132 (week closest to week 132) and baseline through week 156.
- Percentage of subjects with persistent active exudation on SD-OCT from baseline through weeks 48-57 (week closest to week 52), baseline through week 104 and baseline through week 156.

- Percentage of subjects with persistent leakage on fluorescein angiography from baseline through weeks 24-28, baseline to weeks 48-56, baseline to weeks 72-82, baseline to week 104, baseline to weeks 128-132 and baseline to week 156.
- CNVM lesion size at baseline, compared to baseline to weeks 24-28, baseline to weeks 48-56, baseline to weeks 72-82, baseline to week 104, baseline to weeks 128-132 and baseline to week 156, as determined by fluorescein angiography.
- Mean change in central foveal thickness by SD-OCT from baseline to weeks 48-57, baseline to week 104 and baseline to week 156.
- Mean change in BCVA by ETDRS letter score from baseline through weeks 24-28, baseline through weeks 48-56, baseline through weeks 72-82, baseline to week 104, baseline through weeks 128-132 and baseline to week 156.

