### Ocular Imaging

- Fundus Photography (FP) and Fluorescein Angiography (FA)- The anatomical state of the retinal vasculature of the study eye will be evaluated by fundoscopic examination, FP and FA. As well, as a measurement of the CNVM size performed at Screen, between weeks 24-28, 48-57, between weeks 72-82, between weeks 104, between weeks 124-128 and week 156.
- Optical Coherence Tomography (All Study Visits) – Ocular morphology will be evaluated using the Heidelberg Spectralis SD-OCT on the study eye. All SD-OCT images will be captured using the most current software. All SD-OCTs will be electronically archived at the site as part of the source documentation.
- Auto Fluorescence (AF) (All Study Visits) – Ocular morphology will be evaluated using the Heidelberg Spectralis on the study eye. All AF images will be captured using the most current software. All AF's will be electronically archived at the site as part of the source documentation

\*See Appendix E for Imaging Guidelines

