### Procedures performed at Endpoint Visits (if separate from a scheduled visit)

- Floating Endpoints (also known as the Biological Endpoints): ETDRS visual acuity, SD-OCT, AF, FP and FA
- Hard Endpoints: ETDRS visual acuity, SD-OCT and AF

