### **Endpoint Visits:**

Few completed prospective trials have employed a treat and extend protocol. Therefore, there is little data regarding optimal endpoint usage. These endpoints will allow comparison of data from each cohort.

1. **Floating Endpoints** (also known as the Biological Endpoints): Analyses will be performed between weeks 24-28, between weeks 48-57, between weeks 72-82, week 104, between weeks 128-132 and week 156 (range to be determined by timing of last injection). If more than one possible endpoint exists, the time point closest to week 26, week 52, week 78, week 104, week 130 or week 156 will be used. This will be applied to both Cohort A and B, but likely to be most important for Cohort B. All endpoints are measured 4 weeks following the last injection.
2. **Hard Endpoints:** analyses will be performed at week 52 (day 365 $\pm$  7 days), week 104 (day 730  $\pm$  7 days) and week 156 (day 1095)

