  - o Once a dry macula is again achieved the interval between visits will extend by 1-week intervals.
  - o If subject again shows signs of recurrent exudative disease, interval will be by 1 week until dry or subject is back at 4 week interval
  - o Once macula is again dry, treatment interval remains at the same interval for 1 more treatment, after which the treatment interval will be increased by 1-week intervals if the macula remains dry.
    - If patient shows signs of exudative disease 3 times at a certain interval, interval will be decreased by 1 week intervals until the macula is dry AND then remain at this reduced interval for 3 sessions then re-start the treat and extend protocol (meaning extend by 2 week intervals at every visit a dry macula is achieved.
- **Endpoint Measurements:** Additional visits will be scheduled 4 weeks post injection within the "quarterly report" windows defined below. In the event that two possible additional sessions (4 weeks post injection) can be scheduled within a quarterly window, schedule the session which falls closest to the 26 week, 52 week, 78 week, 104 week, 128 week and 156 week marks; if the two sessions are equally spaced around an endpoint, use the earlier. Refer to protocol for visit windows for floating endpoint visits. BCVA, SD-OCT, AF and FA/FP will be performed at the floating endpoint visits.
  - Hard-endpoints will be additional visits at week 52, week 104, and week 156 (± 7 days). BCVA, AF and SD-OCT will be performed at the hard end point visits.

1. Performed at week 104, week 128 & week 156 2. Study drug injection not administered at week 156 3. Optional

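### The count of office visits and imaging does not exclude endpoint-only visits, so through week 104 it understates the visit and scan reduction in extended Cohort B subjects

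*Combined protocol and SAP*

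**What the plan says.** Sections 2.2, 3.4.2 and 4.8.3 list the same secondary outcome: "Total number of office visits and imaging studies performed from baseline through weeks 24-28 (week closest to week 26", and then through the later windows, week 104 and week 156. None of the three excludes any type of visit. Section 4.8.1 leaves statistical detail to a Statistical Analysis Plan, but the available text contains no counting rule.

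The plan also creates visits that serve measurement only. The Cohort 2 (treat-and-extend) notes in Appendix A say of the floating endpoints: "Additional visits will be scheduled 4 weeks post injection". Of the fixed dates they say: "Hard-endpoints will be additional visits at week 52, week 104, and week 156". Section 4.5.1 has a separate procedure list headed "Procedures performed at Endpoint Visits (if separate from a scheduled visit"). For the fixed dates it reads "Hard Endpoints: ETDRS visual acuity, SD-OCT and AF"; floating visits add fundus photography and fluorescein angiography (FP/FA). No injection is listed for either kind. At ordinary visits the same two scans are routine: "Optical Coherence Tomography (All Study Visits") and "Auto Fluorescence (AF) (All Study Visits").

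On timing, the Endpoint Visits text in Section 4.8.3 says "All endpoints are measured 4 weeks following the last injection". It applies floating endpoints to both cohorts and expects them to matter most in Cohort B.

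**The concern.** Section 3.2 names fewer visits and fewer treatments as what the trial specifically evaluates, and the rationale in Section 3.3 includes tests in the burden to be reduced. A visit that exists only because the trial needs a measurement is not part of the burden of the treat-and-extend regimen.

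Cohort A is seen and injected every 4 weeks. Each of its visits is already 4 weeks after an injection, and weeks 52 and 104 are ordinary visits, so it needs no endpoint-only visit through week 104. A Cohort B subject on a longer interval does need them, and each brings an SD-OCT and an AF session. Counting everything performed charges these to one arm only. Two analysts working from the same subject could report different reductions, and the trial is open label, so the choice should be fixed before analysis.

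**Working it through.** The plan states no expected visit count or reduction, so there is no figure to reproduce. The schedules can be enumerated directly.

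**Inputs**
- Cohort A: a visit every 4 weeks (Section 3.2, Appendix A).
- Cohort B: visits at weeks 0, 4 and 8; intervals lengthen by 2 weeks while dry, to at most 12 weeks; recurrence rules as in Section 3.2.
- Floating endpoint: injection + 4 weeks, inside weeks 24-28, 48-57 or 72-82, nearest to 26, 52 or 78 (Section 4.8.3).
- Hard endpoint: week 52. Week 104 is a planned visit for every subject (Section 2).

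**Conventions assumed:** nominal dates; screening and Day 7 left out; an endpoint within 1 week of another visit is taken at that visit; no separate floating visit for week 104.

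**Formula:** reduction = 1 − (Cohort B visits ÷ Cohort A visits).

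**Cohort A:** weeks 0, 4, …, 104 = 27 visits, of which 14 by week 52. Endpoint-only visits: 0.

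**Cohort B, fastest path:** weeks 0, 4, 8, 14, 22, 32, 44, 56, 68, 80, 92, 104 = 12 visits, of which 7 by week 52. Endpoint-only visits: week 26 (22+4), week 48 (44+4), week 52 (hard) and week 72 (68+4) = 4, of which 3 by week 52.

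| Through | Regimen visits only | All visits | Loss |
|---|---|---|---|
| Week 52 | 1 − 7/14 = 50.0% | 1 − 10/14 = 28.6% | 3/14 = 21.4 points |
| Week 104 | 1 − 12/27 = 55.6% | 1 − 16/27 = 40.7% | 4/27 = 14.8 points |

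SD-OCT and AF sessions move one for one with visits. FP/FA does not: after screening, Cohort A and this path each have four planned sessions through week 104.

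**Other conventions, same path**
- Day 7 counted in both arms. Week 104: 1 − 13/28 = 53.6% to 1 − 17/28 = 39.3%. Week 52: 1 − 8/15 = 46.7% to 1 − 11/15 = 26.7%.
- Extension starting only after a week 12 visit. Week 104: 13 + 2 against 27, 51.9% to 44.4%. Week 52: 8 + 1 against 14, 42.9% to 35.7%.
- A separate week 104 floating visit at week 96 (92+4). Week 104: 1 − 17/27 = 37.0%.

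**Shorter limits, week 104.** Here an eye is assumed dry only up to a fixed interval, and the Section 3.2 recurrence rules are applied with extension from week 8.

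| Longest dry interval | Regimen + endpoint-only | Reduction | Loss |
|---|---|---|---|
| 10 weeks | 13 + 4 | 51.9% to 37.0% | 14.8 points |
| 8 weeks | 15 + 3 | 44.4% to 33.3% | 11.1 points |
| 6 weeks | 18 + 3 | 33.3% to 22.2% | 11.1 points |
| 4 weeks | 25 + 0 | 7.4%, unchanged | 0 |
| Never extended | 27 + 0 | 0%, unchanged | 0 |

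**Stop day.** The plan does not say whether the year 1 count ends on the subject's own floating date or at week 52. On the fastest path, the all-visits count is 7 + 2 = 9 if it stops at week 48 (1 − 9/14 = 35.7%) and 10 if it stops at week 52 (28.6%), with Cohort A at 14 both times. For the first window, Appendix A aims at week 24 in Cohort A and week 26 in Cohort B.

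**The case against.** The best reply is that counting visits performed is a legitimate definition, that this is a secondary outcome with no stated test or margin, and that the bias is conservative. A rule may also exist in a Statistical Analysis Plan outside the available text, and the separate procedure list in Section 4.5.1 means both totals could be tabulated anyway. All of that limits the weight of the point. It does not remove it: as written, the count mixes trial procedure with regimen burden in one arm only.

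The reply is also right that the size depends on conventions. The 56%-to-41% figure leaves out Day 7, which is a post-baseline visit with scans in both arms, so it is not a fully literal count. The Cohort 2 table in Appendix A can be read as placing a week 12 visit before the first extension, which cuts the week 104 loss to 2/27 = 7.4 points. If intervals are simply held constant once reached, without modelling recurrences, the shorter-interval losses change: 14.8 points at 6 and 8 weeks, 11.1 at 10. The ±7-day windows can merge some visits.

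A reader might infer that four endpoint-only visits, or 14.8 points, is a ceiling through week 104. The documents do not support that: it depends on absorbing the week 104 floating endpoint into the planned visit, and a week 96 visit would be a fifth. Nor does the mismatch in the third-year target (week 128, 130 or 132 in different places) add to the size; it needs tidying, but no effect on the count has been shown.

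**Conclusion.** The point holds. Through week 104, an all-visits count understates the visit and SD-OCT/AF reduction for Cohort B subjects whose extended schedules require separate endpoint visits. The direction was the same under every convention tried; the size was not. On the fastest path the week 104 loss is about 15 points (7 if extension starts after week 12, 19 with a week 96 visit: 55.6 − 37.0 = 18.6). At week 52 it is about 21 points (7 with the later start). A subject never extended loses nothing.

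These are single-path illustrations on nominal dates. It would be tempting to read them as the expected bias in the cohort comparison, but the distribution of intervals is not in the documents, so no cohort average can be stated. Nor does the point suggest a false benefit: the error runs against Cohort B. Injection counts and the acuity primary are unaffected, and planned FP/FA is matched on the fastest path. The plan should be changed, but the main comparison does not depend on it.

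**What to change.** In Sections 2.2, 3.4.2 and 4.8.3:

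1. Define the main burden count as visits, and SD-OCT and AF sessions, at regimen-scheduled visits. Include week 104 in both arms and exclude endpoint-only visits.
2. Report the all-visits total beside it.
3. State that endpoint FP/FA and the Day 7 visit are handled the same way in both arms.
4. End each windowed count on one common calendar day in both arms, for example day 365 for year 1, with one stated day for each other window.

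The cost is one visit-type flag (regimen or endpoint-only) and a second tabulation. No assessment is added and no treatment rule changes.

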#### **Evidence of recurrent exudative activity**

Clinical evidence of recurrent exudative disease activity requiring reducing the interval between treatments includes any of the following:

1. Evidence of subretinal or intraretinal fluid on SD-OCT which is *not* classified as small intraretinal cystic areas unrelated to active exudative AMD (Appendix D) or minimal increased retinal thickening by SD-OCT without definitive intraretinal or subretinal fluid
2. New macular hemorrhage related to active exudative AMD.
3. ETDRS VA loss of 5 letters from the previous measurement due to neovascular AMD disease process with corresponding SD-OCT evidence of fluid in the macula.
4. Increase in CRT of 50 microns due to active exudative AMD.

The isolated presence of a PED, or enlargement of a PED, does not constitute evidence of exudative disease activity.

If an eye has an ETDRS VA decrease of  $\geq 4$  lines (20 letters) or a subretinal macular hemorrhage of 1DD or larger, at any point during the trial, the subject will subsequently be treated with ranibizumab every 4 weeks.

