## **4. MATERIALS AND METHODS**

### **4.1 SUBJECTS**

#### **4.1.1 Subject Selection**

60 subjects from approximately 4 sites in the United States will be enrolled. Eligible subjects who have provided informed consent will be screened for eligibility before the initiation of any study procedures. Screening evaluations may be performed at any time within the 14 days preceding Day 0. Subjects must have wet macular degeneration secondary to age, with no prior treatment; with disease activity seen on SD-OCT. Subjects can only have one eye in the study, if both eyes are eligible to be in the trial the investigator will determine which eye will be in the study (study eye). Genentech will supply drug for the non-study eye (fellow eye) if needed. Subjects will be randomized in a 1:2 ratio so that:

- 20 subjects will be randomized to the monthly arm (Cohort A)
- 40 subjects will be randomized to the TREX arm (Cohort B)

\*See Appendix A, the study flow chart, for screening assessments.

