## **4.2 METHOD OF TREATMENT ASSIGNMENT**

Subjects will receive open-label IVT of 0.5 mg ranibizumab. Subjects will be randomized into a 1:2 ratio that will occur at Day 0.

- Cohort A – Subjects will receive monthly treatment of 0.5 mg IVT ranibizumab for 100 weeks. Starting at week 104 subjects will receive PRN IVT ranibizumab for another 56 weeks (total of 156 weeks)
- Cohort B – Subjects will receive 0.5mg IVT ranibizumab for 3 a minimum of consecutive visits (visit 2, 4 & 5) followed by a treat and extend protocol in which follow-up intervals are increased when there is no clinical and SD-OCT evidence of disease activity by 2-week intervals. Starting at week 104, if a subject has achieve the 12 week interval they will switch to monthly visits with PRN IVT ranibizumab through week 156. If a subject has not achieved a dry macula they will continue the treat and extend protocol until the 12 week interval is met and then switch to monthly visits with PRN IVT ranibizumab.

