#### **4.8 STATISTICAL METHODS**

##### **4.8.1 Analysis of the Conduct of the Study**

The analysis of data from week 52, week 104 and week 156 treatment period will be performed when all subjects have either completed the visit at week 52, week 104 and week 156 or discontinued early from the study.

The analysis of complete data (week 156) for the study will be performed when all subjects have either completed the visit at week 156 or discontinued early from the study, all data collected from the study are in the database, and the database is locked. Aggregate results of the week 52, week 104 and week 156 analysis, summarized by treatment group, may be reported to the public before completion of the study.

Descriptive summaries will include the mean, standard deviation, median, and range for continuous variables, counts and percentages for categorical variables.

Unless otherwise specified, all statistical tests are two sided. Detailed specifications of the statistical methods are described in the Statistical Analysis Plan.

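### Baseline adjustment is not prespecified for central foveal thickness; adjusting for Day 0 thickness would make the arm comparison more precise at no cost

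*Combined protocol and SAP*

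**What the plan says.** CFT appears in sections 2.2, 3.4.2 and 4.8.3, each time as "Mean change in central foveal thickness by SD-OCT from baseline to weeks 48-57, baseline to week 104 and baseline to week 156". No estimator, model, covariate or test is attached to it.

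The concrete statistical content of section 4.8.1 is general: "Descriptive summaries will include the mean, standard deviation, median, and range for continuous variables", together with "Unless otherwise specified, all statistical tests are two sided". It mentions reporting by treatment group and leaves the detailed methods to a Statistical Analysis Plan. No such detail for CFT is in the supplied text.

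On design, section 4.1.1 sets 20 eyes in Cohort A and 40 in Cohort B. Section 4.2 says "Subjects will be randomized into a 1:2 ratio that will occur at Day 0" and names no stratification factor. Entry needs disease activity on SD-OCT (4.1.1) and accepts any CNVM lesion type (4.1.2), with no lower or upper thickness limit. The visit schedule in Appendix A has SD-OCT at Screening, Day 0 and every later visit, and Appendix E asks for foveal thickness at every visit. Baseline CFT is therefore available for every eye.

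**The concern.** CFT is the only continuous SD-OCT outcome in the plan; the other SD-OCT outcome, persistent exudation, is a percentage. It is therefore the natural place to see whether extending the interval controls the anatomy as well as monthly dosing does.

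Eyes may enter at any thickness, and both schedules aim to dry the macula for two years. If follow-up thickness is less spread out than baseline thickness and only loosely related to it, change from baseline largely reflects where the eye started. With 20 and 40 eyes, a chance difference in mean baseline thickness would then add noise to a simple contrast of mean changes. A model that includes baseline removes most of that noise.

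What is at stake is the width of the interval around the arm difference. There is also a smaller point. The trial is open-label, and aggregate week 52 and week 104 results may be released before completion (4.8.1). If adjustment is left open, it could be decided after the baseline imbalance is known.

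**Working it through.** **No plan figure to reproduce.** The supplied text gives no SD, correlation, effect size, alpha or power for CFT. The only figures to check are the arm sizes: 60 split 1:2 gives 20 and 40.

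**Inputs.** From the documents: n = 20 and 40, two-sided tests. Assumed: 95% intervals; baseline SD *sb* = 80-140 µm; follow-up SD *sf* = 40-70 µm; baseline to follow-up correlation *ρ* = 0-0.4; the same SDs and correlation in both arms; no dropout.

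**Formulas.**
- Allocation factor: k = √(1/20 + 1/40) = 0.274.
- Unadjusted: Var(change) = sb² + sf² − 2ρ·sb·sf.
- Adjusted for baseline: residual variance = sf²(1 − ρ²).
- Half-width = 1.96 × k × SD.
- Share of the unadjusted sampling variance due to chance baseline imbalance = 1 − adjusted variance / unadjusted variance.

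The unadjusted variance minus the adjusted variance equals (sb − ρ·sf)², which cannot be negative. Under these assumptions adjustment therefore cannot lose precision, apart from the one degree of freedom it uses.

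**One case in full** (120 / 50 / 0.2). Var(change) = 14,400 + 2,500 − 2,400 = 14,500, SD 120. Adjusted variance = 2,500 × 0.96 = 2,400, SD 49. Half-widths are 65 and 26 µm. Share = 1 − 2,400/14,500 = 0.83.

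**Across the assumed range.**

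| sb / sf / ρ | SD of change | Adjusted SD | Half-width, change (µm) | Half-width, adjusted (µm) | Share |
|---|---|---|---|---|---|
| 140 / 70 / 0 | 156.5 | 70.0 | 84 | 38 | 0.80 |
| 140 / 40 / 0 | 145.6 | 40.0 | 78 | 21 | 0.92 |
| 120 / 50 / 0.2 | 120.4 | 49.0 | 65 | 26 | 0.83 |
| 80 / 40 / 0.4 | 73.8 | 36.7 | 40 | 20 | 0.75 |
| 80 / 70 / 0.4 | 82.6 | 64.2 | 44 | 34 | 0.40 |

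The half-width is 40-84 µm unadjusted and 20-38 µm adjusted. The ratio of standard errors runs from 1.3 (80/70/0.4) to 3.6 (140/40/0).

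**When baseline imbalance is more than half of the variance.** Setting the share to 0.5 and solving for sf/sb gives break-even ratios of 1.00 at ρ = 0, 0.85 at 0.2, 0.80 at 0.3, 0.76 at 0.4, 0.73 at 0.5 and 0.71 at 0.7. Below the break-even the share exceeds half; above it, it does not. Over a wider grid (sf/sb 0.4-1.0, ρ 0-0.7) the share runs from 15% to 86%.

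**Less favourable cases.** With sb = 100 µm, the standard error of the arm difference falls from 25.1 to 19.0 µm at sf/sb = 0.8, ρ = 0.5; from 27.4 to 23.7 µm at 1.0, 0.5; and from 21.2 to 19.6 µm at 1.0, 0.7. The gain shrinks but remains.

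**Validity of the unadjusted contrast.** In 20,000 simulated trials per scenario with no arm effect, the mean contrast was about 0 and type I error was 4.7-5.1%. A separate simulation of 4,000 trials at 120/50/0.2 gave SDs of the arm difference of 32.8 µm unadjusted and 13.5 µm adjusted. The formulas give 0.274 × 120.4 = 33.0 and 0.274 × 49.0 = 13.4, so the cost of estimating the slope is negligible.

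**The case against.** **The plan has not chosen an unadjusted comparison.** A reader might infer that it has. It has not: a mean change from baseline defines an endpoint, is compatible with a baseline-adjusted estimate, and the methods are left to a Statistical Analysis Plan. This objection stands. What can be said is that the supplied text does not prespecify adjustment. The same silence covers the other outcomes.

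**The size of the gain is not in the documents.** It is tempting to say that the arm contrast is mostly chance baseline imbalance. That is a statement about unknown SDs, and it fails within the assumed range (share 0.40 at 80/70/0.4). It is also a share of sampling variance, not of the contrast, which would include any real effect. The protocol itself leaves room for wider follow-up spread. Under section 3.2 a dry macula may keep a pigment epithelial detachment, small cystic areas or minimal thickening, and from week 104 many eyes move to PRN treatment. This objection stands as to size, but not as to direction.

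**Imbalance does not pass through in full.** Given a baseline imbalance, the expected shift in the change contrast is 1 − ρ·sf/sb of it: 0.92 at 120/50/0.2 and 0.65 at 80/70/0.4. Nor is baseline ignored, since it is subtracted to form the change.

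**The 50-micron figure is not a yardstick here.** Section 3.2 lists "Increase in CRT of 50 microns due to active exudative AMD" as a sign of recurrence within one eye. It is not a margin for a difference between arm means, so how often chance produces a 50 µm arm difference should not be read against it.

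**Other outcomes cover anatomical control.** Persistent exudation, leakage and lesion size are also listed. That lowers the weight of the point but does not remove it.

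**Conclusion.** The point holds as a conditional gain in precision. The supplied text specifies CFT only as mean change with descriptive summaries and states no baseline adjustment, although the covariate is recorded in every eye and the arms are small. Adjustment was more precise in every scenario computed. The half-width falls from 40-84 µm to 20-38 µm under the assumed SDs and correlations, and the gain is small if follow-up spread is close to baseline spread. These figures assume equal SDs and correlation in the two arms and full follow-up. Available-case analysis (4.8.4) with dropout would widen both intervals.

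A reader might go further and infer bias or false anatomical findings. The documents do not support that: under randomisation the unadjusted contrast is unbiased and its type I error is correct. A reader might also carry the figures over to lesion size ("CNVM lesion size at baseline, compared to baseline to weeks 24-28"). The argument from drying concerns thickness, and no gain has been quantified for lesion size.

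Weight: modest. It is one secondary outcome, with a fix that costs nothing.

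**What to change.** Add to section 4.8.3 or the Statistical Analysis Plan: at weeks 48-57, 104 and 156, estimate the between-arm difference in CFT by linear regression of follow-up CFT on arm and Day 0 CFT, with a 95% CI, and report raw mean changes by arm alongside. State that Day 0 is the baseline, because CFT is also measured at Screening.

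The target is still the difference in mean change: regressing change instead of follow-up value on the same two terms gives the same arm coefficient. The model needs the same eyes as the change score, those with both a baseline and a follow-up value, so it adds no missing data.

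Lesion size may be handled the same way with its screening value as covariate, as an option rather than on the strength of these figures.

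Cost: one sentence, one model per time point, one degree of freedom, no new data.
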